4.4.2 Data Collection and Follow-up for Withdrawn Subjects

When a patient withdraws or is withdrawn from the trial, the Investigator shall record the withdrawal reason(s) in the source documents and CRF. Whenever possible, all patients who prematurely withdraw from the trial will undergo all assessments at the early termination visit.

If a patient is discontinued due to an AE, the event will be followed until it is resolved or in the opinion of the PI the patient is determined to be medically stable. Every effort will be made to undertake protocol-specified safety follow-up procedures. Patients who fail to return for final assessments will be contacted by the site study staff to be reminded of the necessary follow-up. As it is vital to obtain follow-up data on any patient withdrawn because of an AE or SAE, follow-up due diligence documentation will consist of 3 phone calls followed by 1 registered letter to the patient's last known address. In any case, every effort must be made to undertake protocol-specified safety follow-up procedures.

5 Study Drug

5.1 Description

GAMUNEX-C is clear a ready-to-use sterile solution of human immune globulin protein for intravenous administration.

5.2 Treatment Regimen

Patients will maintain their stable dose of antiepileptic medications while receiving IVIG or placebo. Patients will be randomized (1:1 ratio) to receive IVIG or placebo (normal saline). The IVIG or placebo dose will be determined based on ideal weight with a dose not to exceed 80 grams. Patients will be given 650 mg acetaminophen (Tylenol®) and Diphenhydramine (Benadryl®) 25 mg PO PRN, may repeat once after 30 minutes if ineffective, 30 minutes prior to IVIG or placebo administration at

every infusion. Patients will receive IVIG or placebo (0.5g/kg) daily for 1 day [week 1 day 1], then they will receive IVIG or placebo (1g/kg not exceeding 80 gr) daily for 1 day [week 1 day 2]. Patients will also receive 500 ml normal saline before and after the higher dose infusion of 1g/kg. Then once every 2 weeks patients will receive 0.6g/kg IVIG or placebo for 4 weeks [week 3 and 5] for 2 infusions. After completion of all 4 infusions all patients will be again evaluated at Mayo Clinic [week 6].

The primary aim is to demonstrate the efficacy of IVIG relative to placebo in reducing or stopping seizures [$\geq 50\%$ reduction in seizure frequency] in patients with VGKC Ab associated autoimmune epilepsy. At the end of the 5 week trial, all patients in the initial placebo group (n=15) will receive, in open label fashion with the same premedications and prehydration protocols IVIG. To help speed up the transition for the placebo group, 1 person from the Mayo study staff, not in direct contact with patients or assessment procedures, will be unblinded, to allow for scheduling with Option Care for the future home infusions. Mayo study staff will work with Option Care to get the infusions scheduled for the placebo to IVIG group as soon as possible after the patient's 6 week visit to Mayo Clinic. Option Care home infusion agency will administer these patients IVIG (0.5g/kg not exceeding 80 gr) 1 day [week 7 day 1] then IVIG (1g/kg not exceeding 80 gr) for 1 day [week 7 day 2], then once every 2 weeks for 4 weeks (0.6g/kg IVIG) [week 9 and 11]. After completion of all 4 IVIG infusions these 15 patients will be again evaluated at Mayo Clinic [week 12].

5.3 Method for Assigning Subjects to Treatment Groups

All patients who are cleared for randomization by their Principal Investigator (PI) or the Sub-Investigator will be randomized on Day 1. The research pharmacy will be performing the 1:1 (drug/placebo) randomization. All patients must remain on randomized treatment assignment until their EOS or Early Termination (ET) Visit.

5.4 Preparation and Administration of Study Drug

- Preparation of the study drug will be done at the research pharmacy
- The drug or placebo will be placed in bags and sent to the infusion center for administration.
- Contact names and Phone number for the Research Pharmacy:

[REDACTED]

5.5 Prior and Concomitant Therapy

- Medication history will be collected for the 2 years prior to entering the trial
- Concomitant medical therapy will be collected throughout the entire year of the trial
- Study subjects are not allowed to start any new immunosuppressant therapy or change their antiepileptic medications during their participation in the primary aim of the trial when they are receiving the IVIG or placebo

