4.1 Inclusion Criteria

- Seropositivity for VGKC complex antibodies (value $>0.1\text{nM}$; normal $\leq 0.02\text{nM}$) or positive for LGI1/CASPR2 Ab by CBA.
- And ≥ 2 seizures per week (mean of total over 1 week)
- Male or female between the ages of 18 and 85 years of age
- Women and men of child bearing potential must agree to use a reliable form of contraception throughout the course of the study.
- Homecare treatment agency available at place of residence, or agreeable to travel to Mayo Clinic in the rare event of unavailability of the homecare agency. (This information will be known by the patient and study team before consenting to the study).
- On a stable dose of antiepileptic medications (unable to change while receiving IVIG/placebo) or on no treatment

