4.2 Exclusion Criteria

- History of thrombotic episodes within the 2 years prior to enrolment
- History of status epilepticus within the last year
- Known allergic or other severe reactions to blood products including intolerance to previous IVIG
- Previous adequate trial of IVIG as determined by the Principal Investigator
- IgA deficiency
- Prior failed trial of high dose steroid (prednisone $>60\text{mg}$ daily or methylprednisolone $>1\text{g}$ weekly for >2 weeks)
- Reproductive status:
 - Women who are pregnant,
 - Women who are breastfeeding,
 - Women and men of childbearing potential who are unwilling or unable to use an acceptable method of birth control to avoid pregnancy for the entire study period, as evaluated by the investigator. (Women of non-childbearing potential are those that have a history of hysterectomy, bilateral oophorectomy, or are postmenopausal with no history of menstrual flow for > 12 months prior to screen visit.)
- Any surgical procedure (except for minor surgeries) within 4 weeks prior to baseline.
- Evidence of serious uncontrolled concomitant diseases that may preclude patient participation (physician determined), as described; Other nervous system disease, cardiovascular disease, hematologic/hematopoiesis disease, respiratory disease, muscular disease, endocrine disease, renal/urologic disease, digestive system disease, congenital or acquired severe immunodeficiency
- Known active infection (excluding fungal infections of nail beds or caries dentium) within 4 weeks prior to baseline.
- Evidence of chronic active hepatitis B or C.
- Active ischemic heart disease in the past year prior to baseline.
- Patients should not have severe renal or hepatic disease (determined by treating physician).
- Severe hypertension (diastolic pressure >120 mmHg or systolic >170 mmHg).

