4.3 Subject Recruitment, Enrollment and Screening

Since our preliminary data indicate a high likelihood of response (80-100%) for patients with VGKC Abs we intend to randomize 30 patients to allow a powered study. Patients will be identified through Mayo Clinic's Neuroimmunology Laboratory [100,000 patients sera tested annually for neural

autoantibodies (~10,000 positive) on a clinical service basis], Autoimmune Neurology Clinic's close interactions with the Epilepsy neurology groups, and referrals through ClinicalTrials.gov website. Patients will be asked to keep a daily seizure diary (minimum of 1 week), before they come for their first evaluation at Mayo Clinic.

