6.1 Visit 1 (Screening)

The following will occur at this visit and last up to 4 hours

- Review of medical history
- Review of past and current medication history
- Vital signs (blood pressure, temperature, heart rate, breathing rates, height and weight)
- Neurologic examination
- Undergo memory and cognitive function assessments (RBANS/ KOKMEN Neuropsych testing)
- Review seizure diary
- Confirmation of stable dose of antiepileptic medications

After the assessments are complete and if the subject still meets all study inclusion criteria blood will be drawn for testing. The amount of blood drawn will be approximately 6 tablespoons or 90mL.

This blood test will look at the following:

- kidney and liver function
- Blood sugar and electrolytes

- IgA immunoglobulins
- Antibody testing
- A pregnancy test if you are a female and able to become pregnant
- Blood for repository for future testing

6.2 Visit 2 & 3; Week-1 Day 1 and Day 2

Mayo Clinic Infusions

Within a few days after the subjects initial evaluation they will receive the first two infusions at the Mayo Clinic Infusion Center. The first infusion (0.5g/kg) drug or placebo will be followed by the second infusion (1g/kg) being given the very next day.

The IVIG infusion is given over approximately 6-8 hours depending on the dose and rate of the infusion. Prior to the infusion the subject will have an intravenous catheter (IV) placed in the subjects arm which will be removed after each infusion is completed.

The subject will be given IV fluids (500 mls of normal saline) before and after the infusion of 1g/kg. The subject will be given acetaminophen (Tylenol) (to prevent headache) and Benadryl (to prevent allergic reaction) before all infusions. Before, during and after the infusions, the subject's vital signs will be monitored.

6.3 Visit 4 & 6; Weeks 2 & 4

Phone Calls

The subject will receive a phone call from the study coordinator at week-2 and again at week-4. During these phone calls, the study coordinator will review the subjects seizure history, medications changes (started any new or stopped any medication), or had any adverse events (side effects, illness, and/or hospitalizations).

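### Section 5.5 bars any change in antiepileptics but only the start of a new immunosuppressant, so changes to an existing steroid dose before week 6 are not prohibited

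*Combined protocol and SAP*

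**What the plan says.** Four places in the combined protocol and SAP control background antiepileptics:

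- 4.1 Inclusion Criteria: "On a stable dose of antiepileptic medications (unable to change while receiving IVIG/placebo) or on no treatment".
- 6.1 Visit 1 (Screening): "Confirmation of stable dose of antiepileptic medications".
- 5.2 Treatment Regimen: "Patients will maintain their stable dose of antiepileptic medications while receiving IVIG or placebo".
- 5.5 Prior and Concomitant Therapy: "Study subjects are not allowed to start any new immunosuppressant therapy or change their antiepileptic medications during their participation in the primary aim". The sentence goes on to limit the rule to the time when IVIG or placebo is being given.

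Only the last of these mentions immunosuppressants, and it bars only starting a new one. The one steroid exclusion, in 4.2, is "Prior failed trial of high dose steroid", defined there by dose and by more than 2 weeks of treatment. Section 4.4.1 says patients should be told of restrictions on changing concomitant medication but sets none.

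The primary endpoint (3.3, 7.2) is a reduction of at least 50% in seizure frequency. Patients are evaluated and unblinded at week 6.

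**The concern.** Steroids are an active treatment for this disease at this site. Section 1.1 names intravenous methylprednisolone (IVMP) and IVIG as the two standard options, and 23 of the 29 patients in the site's own review received IVMP first. A patient already on a steroid can enter the trial, and two routes then stay open.

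- **Recent start.** A steroid begun shortly before baseline may take effect inside the 6-week window, in either arm.
- **Dose change on study.** An existing dose may be raised, which could create responders, or tapered, which could remove them.

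Either route puts outcomes into the comparison that are not due to IVIG. The most plausible result is a smaller difference between arms, and so lower power in a trial of 30.

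**Working it through.** **1. Does any other section close the gap?** No.

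- The phrase about no treatment in 4.1 belongs to the antiepileptic criterion and does not require patients to be free of immunotherapy.
- Medication review at every primary-aim visit (6.14), reporting of seizure increases to the principal investigator (3.2) and possible withdrawal for a 50% increase (4.4.1) make a change visible but do not bar it.
- Section 7.1 has no rule for a patient whose immunotherapy changed.

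**2. What do the site's data (1.1) show?**

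- IVMP-first responders: 23 − 10 = 13, or 13/23 = 57%, across all antibody types.
- IVIG-first responders: 33% of 6 = 2. The total of 15 agrees with the stated 15 first-agent responders.
- Stated response times: 6 in the first week, 6 in weeks 2 to 4 and 1 at 5 weeks, so 12 of 13 within 4 weeks. At most 2 of these 12 were on IVIG, so at least 12 − 2 = 10 were on IVMP.

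These figures bear on a recent start. The documents give no response rate for a raised dose. For tapers, 1.1 reports relapse on reducing the dose or spacing infusions, but in autoimmune cognitive disorders (25% with seizures) and without timing.

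**3. The plan's own power.** Inputs from 7.1: 70% v 10%, 15 per arm, alpha 5%, Fisher's exact test. Exact two-sided enumeration gives 89.4% (stated 89%). At 12, 17 and 19 per arm it gives 82.6%, 94.8% and 97.5% (stated 82%, 94%, 97%).

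**4. Break-even sizes, which need no assumed share of affected patients.** Let p be the IVIG response rate.

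- Added responders: x is the share of all patients whom the steroid alone would make responders, whatever their arm. The rates become p + (1 − p)x on IVIG and 0.10 + 0.90x on placebo.
- Taper: x is the share of would-be responders who lose their response. Both rates are multiplied by (1 − x).

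Values of x at which power reaches 80%, 15 per arm:

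| Planned rates | Base power | Added responders | Taper |
|---|---|---|---|
| 70% v 10% | 89.4% | 7.5% (72.2% v 16.7%; 0.075 × 30 = 2.2 patients) | 12.3% (1.5 of 12 expected responders) |
| 80% v 10% | 97.5% | 20.9% (84.2% v 28.8%; 0.209 × 30 = 6.3 patients) | 26.6% (3.6 of 13.5) |

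The 80% is the low end of the "high likelihood of response (80-100%) for patients with VGKC Abs" in 4.3. At 12 per arm and 70% v 10%, where base power is only 82.6%, the break-evens are 2.0% and 2.8%, less than one patient each.

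**5. Illustration only.** Assume that a fraction f of patients is affected and that the steroid response is r = 25% or 57%, so x = f × r. The 25% is an assumption; the 57% is the 13/23 above. Power for r = 25%, then 57%:

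| Per arm, rates | f = 5% | f = 10% | f = 20% |
|---|---|---|---|
| 15, 70% v 10% | 88%, 86% | 86%, 82% | 83%, 75% |
| 15, 80% v 10% | 97%, 96% | 96%, 95% | 95%, 90% |
| 12, 70% v 10% | 81%, 79% | 79%, 75% | 76%, 68% |
| 12, 80% v 10% | 94%, 93% | 93%, 90% | 91%, 85% |

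**The case against.** The strongest case against has four parts.

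- **Silence is not permission.** A reader might infer that the protocol allows steroids to be raised or tapered. It does not say so. A new course is already barred on treatment, and 4.4.1 speaks of restrictions on concomitant medication generally. This stands: the accurate statement is that dose changes are not prohibited.
- **The response data do not measure a dose change.** A reader might take 13 of 23, or 12 of 13 within 4 weeks, as the effect of raising a steroid on study. They describe starting treatment. This also stands.
- **The recent-start route is narrow.** Entry needs at least 2 seizures per week on a diary of at least 1 week, so some fast steroid responders would no longer qualify. A patient still seizing after more than 2 weeks at high dose may be judged to have failed steroids and be excluded, although failure is undefined and a partial responder could remain. What is left is mainly short high-dose courses and lower doses. The 57% therefore probably overstates the rate in patients still eligible.
- **The effect on the result is conditional.** At 15 per arm and 70% v 10%, only the most extreme illustrated case falls below 80% power. At 90% v 10%, that same case keeps 98% power with 15 per arm and 95% with 12. Against this, 70% is the rate on which the trial was sized, and 12 per arm is the plan's own dropout scenario.

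None of this supplies the missing rule for an existing dose.

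**Conclusion.** The gap is real but modest. Followed exactly, the plan leaves an active co-treatment uncontrolled up to the week-6 responder assessment while holding antiepileptics fixed.

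The size is unknown, because the documents give neither the share of patients who would enter on immunotherapy nor a response rate for a dose change. The power loss matters mainly near the 70% v 10% planning rate. The break-evens assume a steroid effect that is equally common in both arms and acts regardless of IVIG, and a two-sided test, which is the version that reproduces the stated 89%.

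A reader might also infer a bias in favour of IVIG. The documents do not support that: allocation is randomised and blinded to week 6, and nothing suggests that steroid changes would favour the IVIG arm. Dilution is the most plausible effect, but the direction is not fixed. This is a point to consider, with medium confidence, and not a threat to the trial's validity.

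**What to change.** - **5.5:** Replace the bar on new immunosuppressants with a bar on starting, stopping or changing the dose of any immunotherapy, including corticosteroids, until the week-6 assessments are complete (week 12 for the open-label course). Allow changes for safety, with date and dose recorded.
- **4.1 and 6.1:** Require any existing immunotherapy to be at a stable dose at baseline and confirm it at Visit 1, next to the antiepileptic check.

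This costs almost nothing beyond wording: medication history and review are already scheduled.

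A 4-week pre-baseline stability window is optional and a trade-off. It would cover 12 of the 13 timed first-agent responses (one needed 5 weeks). It equals a look-back length already used in 4.2, "Any surgical procedure (except for minor surgeries) within 4 weeks prior to baseline", although that precedent is not about immunotherapy. Some recent steroid starters would be lost and not merely delayed: after 4 weeks they may have fallen below 2 seizures per week or may meet the failed-steroid exclusion. At a single site recruiting 30, the sponsor should weigh that loss before adding the window.

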5.6 Packaging

- The drug will be shipped by Grifols to the research pharmacy at Mayo Clinic
- The saline placebo will be clear in appearance to match the appearance of Gamunex-C®
- The drug will be shipped in glass vials (20 g, 10 g and 5 g)
- The drug will be mixed in plastic bags for administration at the Mayo infusion center.
- The bags will be labeled by Mayo's Research Pharmacy in accordance with all laws and state "Gamunex-C® or Placebo"

5.7 Masking/Blinding of Study

The entire Mayo study team, investigator, and the nurse administering the drug at Mayo's infusion center will be blinded (double-blind). Only the research pharmacy and one unblinded Mayo study team member without patient contact will know which subjects will be receiving actual drug, and which subjects will be receiving placebo.

5.8 Receiving, Storage, Dispensing and Return

5.8.1 Receipt of Drug Supplies

Grifols will ship the Gamunex-C® to Mayo Clinic's Research Pharmacy in Rochester, MN. Upon receipt of the of the study treatment drug, an inventory must be performed and a drug receipt log filled out by the person accepting the shipment. It is important that the designated study staff counts and verifies that the shipment contains all the items noted in the shipping invoice. Any discrepancies, damaged or unusable study drug in a given shipment will be documented in the study files. The sponsor (Grifols) and the investigator must be notified immediately of any discrepancies, damaged or unusable products that are received.

5.8.2 Storage

The study drug will be stored at the research pharmacy. Temperature logs will be kept and monitored as required.

5.8.3 Dispensing of Study Drug

Regular study drug reconciliation will be performed to document drug assigned, drug dispensed, drug returns, and drug remaining. This reconciliation will be logged on the drug reconciliation form, and signed and dated by the pharmacy and study team.

5.8.4 Return or Destruction of Study Drug

At the completion of the study, there will be a final reconciliation of drug shipped, drug dispensed, drug returns, and drug remaining. This reconciliation will be logged on the drug reconciliation form, signed and dated. Any discrepancies noted will be documented and investigated, prior to return or destruction of unused study drug. Drug destroyed on site will be documented in the study files.

6 Study Procedures

6.1 Visit 1 (Screening)

The following will occur at this visit and last up to 4 hours

- Review of medical history
- Review of past and current medication history
- Vital signs (blood pressure, temperature, heart rate, breathing rates, height and weight)
- Neurologic examination
- Undergo memory and cognitive function assessments (RBANS/ KOKMEN Neuropsych testing)
- Review seizure diary
- Confirmation of stable dose of antiepileptic medications

After the assessments are complete and if the subject still meets all study inclusion criteria blood will be drawn for testing. The amount of blood drawn will be approximately 6 tablespoons or 90mL.

This blood test will look at the following:

- kidney and liver function
- Blood sugar and electrolytes

- IgA immunoglobulins
- Antibody testing
- A pregnancy test if you are a female and able to become pregnant
- Blood for repository for future testing

6.2 Visit 2 & 3; Week-1 Day 1 and Day 2

Mayo Clinic Infusions

Within a few days after the subjects initial evaluation they will receive the first two infusions at the Mayo Clinic Infusion Center. The first infusion (0.5g/kg) drug or placebo will be followed by the second infusion (1g/kg) being given the very next day.

The IVIG infusion is given over approximately 6-8 hours depending on the dose and rate of the infusion. Prior to the infusion the subject will have an intravenous catheter (IV) placed in the subjects arm which will be removed after each infusion is completed.

The subject will be given IV fluids (500 mls of normal saline) before and after the infusion of 1g/kg. The subject will be given acetaminophen (Tylenol) (to prevent headache) and Benadryl (to prevent allergic reaction) before all infusions. Before, during and after the infusions, the subject's vital signs will be monitored.

6.3 Visit 4 & 6; Weeks 2 & 4

Phone Calls

The subject will receive a phone call from the study coordinator at week-2 and again at week-4. During these phone calls, the study coordinator will review the subjects seizure history, medications changes (started any new or stopped any medication), or had any adverse events (side effects, illness, and/or hospitalizations).

6.4 Visit 5 & Visit 7; Week-3 and Week-5

Mayo Clinic Infusion Center

Week-3 infusion (0.6g/kg drug or placebo) will be given 2 weeks following the 2nd infusion. Week-5 (0.6g/kg drug or placebo) infusion will be given 2 weeks after the 3rd infusion (total of 5 weeks).

6.5 Visit 8; Week 6

Mayo Clinic Examination and Unblinding.

During this visit, patients will be seen in clinic. All required assessments will be documented and signed.

- Review current medication history
- Vital signs (blood pressure, temperature, heart rate, breathing rates, and weight)
- Neurological Examination
- Undergo memory and cognitive function assessments (RBANS/KOKMEN- Neuropsych testing)
- Blood draw to check antibody levels.
- Review Seizure Diary

Then, the study physician and the subject will be unblinded.

If the study subject received placebo, they will be given IVIG in an open label fashion through Option Care Home Infusion service using the same dose and schedule as used for the first portion of this study. The last 4 IVIG infusions for those 15 patients, who received placebo for the first 4 treatments, will be given at the patient's home or clinic near their home. These infusions will be given per Option Care's standard operating procedure. In this study we are going to utilize the home care network of Option Care nationwide. Therefore one of the inclusion criteria is that the home treatment network is available where the patient lives.

If the study subject received IVIG, this will be their Research clinic visit, and they will NOT receive any more infusions for the study, they will only receive the phone calls for long term follow up and proceed to VISIT 16, 26 of the tertiary aim.

6.6 Visit 9 & 10; Week 7: Day 1/Day 2

Option Care Home Infusion

Within a 7-10 days after the subjects Week6 evaluation they will receive the first two infusions through Option Care. The first infusion (0.5mg/kg) IVIG will be followed by the second infusion (1g/kg) being given the very next day.

The IVIG infusion is given over approximately 6-8 hours depending on the dose and rate of the infusion. Prior to the infusion the subject will have an intravenous catheter (IV) placed in the subjects arm which will be removed after each infusion is completed.

The subject will be given IV fluids (500 mls of normal saline) before and after the infusion of 1g/kg. The subject will be given acetaminophen (Tylenol) (to prevent headache) and Benadryl (to prevent allergic reaction) before all infusions. Before, during and after the infusions, the subject's vital signs will be monitored and documented by Option Care. This information will be send to Mayo Clinic for the study records.

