Number of Subjects	30 Subjects
Diagnosis and Main Inclusion Criteria	A diagnosis of autoimmune epilepsy with ≥ 2 seizures per week and seropositivity for VGKC complex antibodies (value $>0.1nM$; normal $\leq 0.02nM$) or positive for LGII/CASPR2 Ab by CBA.
Study Product, Dose, Route, Regimen	Gamunex-C (Immune Globulin IV (Human)) or Placebo, IV infusion of. 0.5g/kg dose one, 1g/kg dose two, 0.6g/kg dose three, 0.6g/kg dose four.
Duration of Administration	5 weeks for IVIG Groups, 12 weeks for placebo crossover
Reference therapy	Placebo
Statistical Methodology	Primary outcome, which is binary variable, i.e. proportion of patients responding to treatment (yes, no) will be estimated along with 95% exact binomial confidence intervals for each arm of the respective study. These proportions will then be compared using Fisher's exact test within the study. Continuous outcomes of interest will be compared using two sample t-test or Wilcoxon rank sum test as appropriate.

1 Introduction

This study evaluates the utility of IVIG in the evaluation and management of patients with suspected autoimmune epilepsy associated with voltage gated potassium channel complex autoantibodies (VGKC Ab).

The described study will be conducted in compliance with the protocol, Good Clinical Practices standards and associated Federal regulations, and all applicable institutional research requirements.

This document is a protocol for a human research study. This study will be carried out in accordance with the applicable United States government regulations and Mayo Clinic research policies and procedures.

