3.2 Study Schematic

Patients will be randomized (1:1 ratio) to receive IVIG or placebo (normal saline). The IVIG or placebo dose will be determined based on ideal weight with a dose not to exceed 80 grams. Patients will be given 650 mg acetaminophen (Tylenol®) and Diphenhydramine (Benadryl®) 25 mg PO PRN, may repeat once after 30 minutes if ineffective, 30 minutes prior to IVIG or placebo administration at every infusion. Patients will receive IVIG or placebo (0.5g/kg) daily for 1 day [week 1 day 1], then they will receive IVIG or placebo (1g/kg not exceeding 80g) daily for 1 day [week 1 day 2]. Patients will also receive 500 ml normal saline before and after the higher dose infusion of 1g/kg. Then, once every 2 weeks [week 3 & 5], patients will receive (0.6g/kg) IVIG or placebo for 4 weeks (2 infusions). After completion of all 4 infusions all patients will be again evaluated at Mayo Clinic [week 6].

The primary aim is to demonstrate the efficacy of IVIG relative to placebo in reducing or stopping seizures [$\geq 50\%$ reduction in seizure frequency] in patients with VGKC Ab associated autoimmune epilepsy. At the end of the 5 week trial, all patients in the initial placebo group (n=15) will receive, in an open label fashion with the same premedications and prehydration protocols IVIG. To help speed up the transition for the placebo group, 1 person from the Mayo study staff, not in direct contact with patients or assessment procedures, will be unblinded, to allow for scheduling with Option Care for the future home infusions. Mayo study staff will work with Option Care to get the IVIG infusions scheduled for the placebo group as soon as possible after the patient's 6 week visit to Mayo Clinic. Option Care home infusion agency will administer these patients IVIG (0.5g/kg) 1 day [week 7 day 1] then IVIG (1g/kg not exceeding 80g) for 1 day [week 7 day 2], then once every 2 weeks for 4 weeks (0.6g/kg IVIG) [week 9 and 11]. After completion of all 4 IVIG infusions these 15 patients will be again evaluated at Mayo Clinic [week 12].

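### Section 6.6 gives the first open-label home infusion in mg/kg, while every other statement of that dose is in g/kg: a 1000-fold contradiction in a dosing instruction

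*Combined protocol and SAP*

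**What the plan says.** After the week 6 visit, patients first assigned to placebo receive four open-label IVIG infusions from a home-infusion agency, at home or at a nearby clinic. The protocol states the first of these doses in several places.

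- Section 6.6, the visit procedure for week 7: "The first infusion (0.5mg/kg) IVIG will be followed by the second infusion (1g/kg) being given the very next day".
- Section 3.2, the schematic, for the same day: "Option Care home infusion agency will administer these patients IVIG (0.5g/kg) 1 day [week 7 day 1".
- Section 5.2, the treatment regimen, for the same day: "Option Care home infusion agency will administer these patients IVIG (0.5g/kg not exceeding 80 gr) 1 day [week 7 day 1".
- Section 6.5, on the open-label course as a whole, says it is given "using the same dose and schedule as used for the first portion of this study".

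The blinded course to which 6.5 points begins with 0.5 g/kg in section 6.2 ("The first infusion (0.5g/kg) drug or placebo will be followed by the second infusion (1g/kg) being given the very next day") and in section 3.2 ("Patients will receive IVIG or placebo (0.5g/kg) daily for 1 day [week 1 day 1"), and section 5.2 agrees. The Study Summary lists the regimen as "0.5g/kg dose one, 1g/kg dose two, 0.6g/kg dose three, 0.6g/kg dose four".

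**The concern.** Section 6.6 is a visit-level instruction, not background text. It governs infusions given away from the study site by an outside agency, whereas the blinded infusions are given at the site's own infusion center from bags made up by the research pharmacy (sections 5.4 and 5.6). If 6.6 is followed, 3.2, 5.2 and 6.5 are broken; if they are followed, 6.6 is broken.

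The first thing at stake is the safety of the patients treated under this text. The second is interpretation. Former placebo patients have seizure, cognitive and antibody assessments at week 12 and enter the one-year follow-up, where relapse is measured against seizure frequency after IVIG. If their course differed from the one the IVIG arm received, the two sets of treated patients would not be comparable in the secondary and tertiary aims.

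**Working it through.** The plan has no calculated figure to reproduce here. The check is a comparison of texts followed by unit conversion.

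**Step 1. Statements of the first-infusion dose**

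| Place | Course | First dose |
|---|---|---|
| Study Summary | regimen | 0.5 g/kg |
| 3.2 | blinded, week 1 day 1 | 0.5 g/kg |
| 5.2 | blinded, week 1 day 1 | 0.5 g/kg |
| 6.2 | blinded, week 1 day 1 | 0.5 g/kg |
| 3.2 | open label, week 7 day 1 | 0.5 g/kg |
| 5.2 | open label, week 7 day 1 | 0.5 g/kg |
| 6.5 | open label | as in the blinded course |
| 6.6 | open label, week 7 day 1 | 0.5 mg/kg |

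Section 6.6 is the only place with a mg/kg figure for this infusion. A fault in reading the PDF is unlikely: the near-identical sentence in 6.2 reads g/kg, and the same sentence in 6.6 gives the second infusion in g/kg.

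**Step 2. Size for the single infusion**

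Ratio = 0.5 g/kg ÷ 0.5 mg/kg = 500 mg/kg ÷ 0.5 mg/kg = 1000.

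Doses are based on ideal weight. The documents give no weights, so 50 to 100 kg is assumed. Volumes use the 10% product strength in section 1.2, about 0.1 g/mL.

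| Assumed weight | 0.5 g/kg | 0.5 mg/kg |
|---|---|---|
| 50 kg | 25 g (250 mL) | 0.025 g (0.25 mL) |
| 70 kg | 35 g (350 mL) | 0.035 g (0.35 mL) |
| 100 kg | 50 g (500 mL) | 0.050 g (0.50 mL) |

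**Step 3. Size for the four-infusion course**

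- Study Summary regimen: 0.5 + 1 + 0.6 + 0.6 = 2.7 g/kg.
- Section 6.6 read literally: 0.0005 + 1 + 0.6 + 0.6 = 2.2005 g/kg.
- Difference: (2.7 − 2.2005) ÷ 2.7 = 18.5%.

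This holds while the 80 g cap does not bind on the 1 g/kg infusion, that is, up to 80 kg. At 100 kg the cap holds that infusion at 80 g. The totals are then 50 + 80 + 60 + 60 = 250 g and 0.05 + 80 + 60 + 60 = 200.05 g, a difference of 49.95 ÷ 250 = 20.0%.

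**Step 4. Reach**

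The open-label course covers the initial placebo group, planned at 15 (sections 3.2 and 5.2). Section 7.1 has treatment unblinded at the week 6 follow-up, and 6.5 places unblinding after the week 6 assessments. Both come before week 7, so the Fisher's exact comparison and its power do not depend on section 6.6.

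**The case against.** The contradiction itself cannot be argued away, but its weight can be.

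- **Internal cues.** Section 6.5 sits directly above 6.6 and ties the open-label dose to the blinded one. Section 5.2 is the dedicated regimen section. Section 6.6 itself says "The IVIG infusion is given over approximately 6-8 hours depending on the dose and rate of the infusion", and the smallest vial listed in 5.6 is 5 g. A careful reader would probably query the text before infusing. This stands, and it lowers the chance that the discrepancy passes unnoticed, but a 1000-fold conflict in a dosing instruction should not depend on someone noticing it.
- **One infusion, not the course.** The factor of 1000 applies to the first infusion only; total exposure differs by about 18.5%. This stands, and the course figure is the more relevant one for comparability.
- **The analysis consequence is conditional.** Nothing shows that a different dose was or would be given. Sections 7.1 and 7.2 describe no model that pools the two groups, and the tertiary assignment is limited to responders without saying whether open-label responders count. This stands in part. Week 12 antibody draws for the placebo group and one-year follow-up of all patients support the reading that both groups contribute, but the plan does not spell it out.
- **Unseen material.** The agency works to its own procedure, cited as appendix 2, which was not available for this review. It may carry an unambiguous dose. That is a reason to check it, not a reason to leave the protocol inconsistent.

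**Conclusion.** The concern holds. The protocol gives two doses, 1000-fold apart, for the same infusion, and the one that stands alone is in the visit procedure for off-site treatment. The text affects every initial-placebo patient who starts the open-label course, 15 as planned and fewer if some withdraw. Total exposure would differ by 18.5%, or about 20% at an assumed 100 kg, where the cap binds.

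The contradiction and the factor of 1000 rest on the text alone; only the gram and milliliter illustrations depend on assumed weights. The primary analysis is unaffected. The effect on the predictor and relapse work is a secondary argument that depends on both groups being used there. The correction should be made, mainly on patient-safety grounds. This review takes no position on which figure is right.

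**What to change.** Reconcile section 6.6 with the Study Summary and sections 3.2, 5.2, 6.2 and 6.5 so that one dose and one unit appear wherever the first infusion is described. The sponsor decides which figure stands. Then confirm that the home-infusion agency's procedure and any order form it uses carry the reconciled text. If any patient has already had the week 7 day 1 infusion, record the dose actually given so that the secondary and tertiary analyses can describe exposure correctly.

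The cost is a one-line protocol correction and one check with the agency. Sample size, the primary analysis and the visit schedule do not change.
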